Statistical Analysis Plan

For CLP 11899

MIND: A Prospective, Multicenter Study of Artemis a Minimally Invasive Neuro Evacuation Device, in the Removal of Intracerebral Hemorrhage

Prepared by: Penumbra Inc.

NCT number: NCT03342664

Date: January 02, 2020

1. Overview

This is a multi-center randomized controlled study designed to compare the safety and efficacy of minimally invasive hematoma evacuation with the Artemis Neuro Evacuation Device to best medical management for the treatment of intracerebral hemorrhage (ICH).

Up to 500 patients will be enrolled from up to 50 global centers (US and OUS). Each site will be limited to a maximum enrollment of up to 120 patients (~20% of total enrollment).

This Statistical Analysis Plan (SAP) will provide details to further elaborate statistical methods as outlined in the protocol and will describe analysis conventions. The SAP will be signed off prior to unblinding.

2. Sample Size

A sample size of up to 500 patients was selected for this study. Based on simulations, this trial has 81% power for a cumulative odds ratio of 1.7 with a one-sided alpha of 0.025. The minimum sample size is 200 patients (approximately 133 MIS and 67 MM).

The Day 180 mRS distribution used for sample size estimation was based on control arm data from the following published studies: MISTIE II (Hanley 2016), STICH (Mendelow 2005), and SICHPA (Teernstra 2003). The distribution of mRS functional outcomes utilized in the sample size estimation is provided in Table 1.

Table 1. Distribution of mRS functional outcomes

mRS Distribution	0	1	2	3	4	5/6
MM	3%	10%	7%	7%	14%	59%
MIS	5%	15%	10%	9%	16%	46%

3. Randomization

Randomization takes place centrally through a commercially available Interactive Web Response System (IWRS). Randomization will occur in a 2:1 ratio to either MIS or MM. The treatment allocation will be balanced by Hemphill Score (0-2, 3-4) and hemorrhage location (primarily lobar, primarily deep).

If a lack of equipoise for randomization between treatment and control occurs during trial execution, the trial randomization assignment will be revised to randomize all patients to the MIS. The minimum sample size for patients assigned to MIS treatment is 133 patients.

4. Interim Analysis

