10.1. Primary Efficacy Analysis

The primary endpoint is the Day 180 global disability assessed via the ordinal modified Rankin score (mRS).

The null hypothesis is that the cumulative odds ratio for mRS at 180 days in the MIS group compared to MM group is less than or equal to 1. The alternative hypothesis is that the cumulative odds ratio for mRS at 180 days is greater than 1. Formally, the null and alternative hypotheses to be tested are as follows:

H0: OR ≤ 1

HA: OR > 1 ,

where OR is the cumulative odds ratio for the mRS at the 180-day follow-up visit, with higher values indicating better outcomes in the MIS group.

Statistical analysis of the primary endpoint will be conducted using a logistic regression analysis of the 180-day mRS scores. The primary efficacy endpoint is met if the overall treatment effect is positive at a one-sided alpha of 0.02. The odds ratio and corresponding 95% confidence interval will be estimated from the proportional odds model. The proportional odds assumption will be assessed visually for the cumulative proportions and odds ratio estimates. The primary analysis will be unadjusted. A secondary analysis model will include the minimization variables of Hemphill Score and hemorrhage location. The mRS scores of 5 and 6 will be combined into a single group for the purposes of endpoint evaluation. Subjects deceased during study follow-up will be scored as mRS 6. As a sensitivity analysis, the mRS scores of 5 and 6 will be evaluated as separate groups.

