10.4. Handling of Multiplicity

There will be no adjustment on the comparison between MIS and MM on the primary effectiveness variable since the primary comparison is specified in the protocol. The following 8 secondary efficacy analyses will be adjusted using the Bonferroni correction and may be used for labeling claims:

- Stroke Impact Scale – Mobility at 180 days
- Stroke Impact Scale – ADLs at 180 days
- Stroke Impact Scale – Mobility at 365 days
- Stroke Impact Scale – ADLs at 365 days
- EQ-5D-5L at 180 days
- EQ-5D-5L at 365 days
- Length of hospital stay
- Length of ICU stay

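### The eight label-claim secondaries are adjusted by single-step Bonferroni; a Holm step-down keeps the same family-wise error bound and can only win as many claims or more

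*SAP*

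**What the plan says.** SAP 10.4 covers multiplicity for efficacy. For the primary it says: "There will be no adjustment on the comparison between MIS and MM on the primary effectiveness variable". For the secondaries it says: "The following 8 secondary efficacy analyses will be adjusted using the Bonferroni correction and may be used for labeling claims". The list has eight items: SIS-Mobility, SIS-ADLs and EQ-5D-5L, each at Day 180 and Day 365, plus length of hospital stay and length of ICU stay.

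Neither SAP 10.4 nor SAP 10.2 describes a step-down rule, an ordering of the eight or any recycling of alpha. The family alpha and its sidedness are not stated, and no simultaneous confidence intervals are planned for the eight. Protocol 10.9 gives no multiplicity rule and leaves further analyses to the statistical plan. Subgroup comparisons (SAP 10.5) and the other safety comparisons (SAP 11.3) are expressly kept out of labeling.

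**The concern.** With eight tests and single-step Bonferroni, the hurdle for each claim stays at alpha/8 even after other claims in the family have been won. Holm relaxes the hurdle as claims accumulate and keeps the same family-wise guarantee. The two methods therefore differ whenever at least one endpoint passes alpha/8 and another falls between alpha/8 and the next Holm threshold.

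What is at stake is the number of label claims the trial can support from this list if the procedure improves several of these outcomes at once. The validity of any claim is not at stake.

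**Working it through.** **The plan's own figure.** No power or adjusted alpha is given for the eight secondaries. The only stated power is for the primary: "this trial has 81% power for a cumulative odds ratio of 1.7 with a one-sided alpha of 0.025". As a check on reading the design, take a fixed-sample proportional-odds calculation with N = 500, r = 2 (2:1) and the MM row of SAP Table 1 shifted by OR 1.7. The information is V = rN/[3(r+1)²] × (1 − Σp̄³), where p̄ is the mean category proportion over both arms. It gives 82.9% at one-sided 0.02 and 85.2% at one-sided 0.025. The stated 81% comes from adaptive simulations that are not in the documents. Nothing below depends on it.

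**Inputs for this point.** The number of tests (8) and the method (Bonferroni) come from SAP 10.4. The rest is assumed, because the documents give no value:
- family alpha two-sided 0.05
- unadjusted power of 50% to 90% for each real effect
- common pairwise correlation 0.3 to 0.7

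**Thresholds.** Bonferroni: 0.05/8 = 0.00625 for all eight. Holm, ordering p-values from the smallest, uses 0.05/(8 − i) for i = 0 to 7: 0.00625, 0.00714, 0.00833, 0.0100, 0.0125, 0.0167, 0.0250, 0.0500. Testing stops at the first failure. If the family alpha were 0.04, Bonferroni would use 0.0050 throughout and Holm would run from 0.0050 to 0.0400.

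**Why Holm cannot lose a claim.** Every Holm threshold is at least alpha/8, so any p-value at or below alpha/8 is also rejected by Holm. This needs no assumption about effects or correlation. In simulation Holm rejected every hypothesis that Bonferroni rejected, in every replicate.

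**Bonferroni power per claim, by hand.** At 80% unadjusted power the mean of the test statistic is 1.960 + 0.842 = 2.802. The critical value at two-sided 0.00625 is 2.734. Power is Φ(2.802 − 2.734) = Φ(0.068), about 53%. The same steps give about 22% from 50% unadjusted power and 69% from 90%.

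**Holm power per claim, by simulation** (200,000 replicates per scenario, correlation 0.3 to 0.7):

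| Real effects | Unadjusted power | Bonferroni | Holm | Gain (points) |
|---|---|---|---|---|
| 2 of 8 | 80% | 53% | 54% | about 1 |
| 4 of 8 | 50% | 22% | 23–24% | 1–2 |
| 4 of 8 | 70% | 40% | 43% | 3 |
| 4 of 8 | 80% | 53% | 56% | 3 |
| 8 of 8 | 50% | 22% | 26–28% | 4–6 |
| 8 of 8 | 70% | 40% | 49% | 9 |
| 8 of 8 | 80% | 53% | 63–64% | 10–11 |
| 8 of 8 | 90% | 69% | 79–81% | 10–12 |

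With all eight real at 80% unadjusted power, expected claims rise from 4.2 to 5.0–5.1.

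**At least one claim.** This probability is identical under the two methods, because Holm's first step is also 0.00625. With all eight real at 80% it is 95.7% at correlation 0.3 and 86.9% at 0.6, for both.

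**False claims.** With four of eight real at 80%, the chance of any false claim among the four nulls rises from 2.4% to 3.5% at correlation 0.3, and from about 1.9% to about 2.8% at 0.7. Both stay inside 5%. If no effect is real, the two methods have the same family-wise error.

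**Role of correlation.** With all eight real at 80%, Holm power per claim goes from 64.4% to 63.9%, 63.1% and 62.0% as correlation goes from 0 to 0.3, 0.6 and 0.8. At 50% it goes from 24.7% to 26.2%, 27.4% and 27.9%. The shift is a few points at most and its direction varies. The number of real effects is what drives the gain.

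**The case against.** Bonferroni is valid, prespecified, simple and conservative. No bias, contradiction or inflated error follows from it, and the sponsor that chose it bears the cost. All of that stands, and it makes this a recommendation and not a correction.

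A reader might go further and infer that power is being given up for nothing. The documents and the arithmetic do not support that:
- Bonferroni has simultaneous confidence intervals that match its decisions; Holm has no equally simple counterpart. The SAP plans no such intervals for these eight, so nothing documented would be lost, but the property is real.
- Holm spends more of the allowed error when some nulls are true, as the false-claim figures show.
- Bonferroni also bounds the expected number of false claims at alpha, and Holm does not. With two of eight real, 80% unadjusted power and correlation 0.7, that number is about 0.038 under Bonferroni and about 0.052 under Holm.

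A reader might also infer that measuring the same scales at Day 180 and Day 365 makes Bonferroni especially wasteful because the tests are correlated. Holm does not use the correlation. The repeated scales matter only in that their effects may well be real together.

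Finally, the largest gains assume that all eight effects are real and well powered. The documents give no effect size, standard deviation or correlation for any of the eight, and enrollment may stop from 200 subjects, so the lower rows of gain are just as relevant.

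**Conclusion.** The point holds as an efficiency improvement. Single-step Bonferroni in SAP 10.4 is valid but less powerful than Holm at the same family-wise bound. That direction is a mathematical fact and rests on no assumption.

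The size does rest on assumptions: two-sided family alpha 0.05, equal effects and correlation 0.3 to 0.7. The gain per real claim is about 1 point with two real effects, about 1 to 3 with four, and about 4 to 11 with all eight at 50% to 80% unadjusted power (10 to 12 at 90%). The chance of at least one claim does not move.

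It would be wrong to read this as a type I error problem or as a flaw that invalidates any claim. The missing family alpha and sidedness, and the absence of any stated gate on the primary, affect Bonferroni and Holm alike. They may matter more than the choice between the two.

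**What to change.** In SAP 10.4, name the Holm step-down procedure in place of the Bonferroni correction, for the same eight analyses at the same family alpha. In the same sentence state that alpha and whether it is one- or two-sided, since neither rule can be applied without it. Report Holm-adjusted p-values. If simultaneous intervals are wanted, give them at the Bonferroni level, and note that they may not match the later Holm rejections.

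Make the change in a revised SAP before unblinding. SAP section 1 sets sign-off before that point and section 17 provides for revision. Adopting Holm after results are known would not be credible.

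The cost is a sentence or two of text, with no new data or patients. The price is the interval mismatch and a somewhat higher, still controlled, chance of a false claim.

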10.5. Efficacy Subgroup Analysis

To evaluate the impact of baseline conditions on treatment effect on functional outcome, subgroup analyses will be performed for the primary efficacy variable, 180-day ordinal mRS. Subgroup comparisons will be considered secondary analyses and will not be adjusted or used for labeling claims. The subgroups below will be used for these analyses:

- **Age** (< 65, or \geq 65)
- **Gender** (Male, or Female)
- **Race/Ethnicity**
- **Baseline Hemphill** (0-2, or 3-4)
- **Site of hemorrhage** (primarily lobar, primarily deep)
- **Geographic Location** (US, OUS)
- **Time from stroke symptom onset to randomization** (below the median, above the median)
- **Time from stroke symptom onset to sheath placement** (below the median, above the median)
- **Baseline GCS for ICH volume 20-30 cc (A x B x C/2)** (GCS \geq 9, GCS \leq 8)

The subgroup analysis will be conducted using regression with terms of treatment group and treatment-by-subgroup interaction. In addition, Hemphill Score and hemorrhage location will be included in the model. The primary statistical inference is the treatment-by-subgroup interaction, which is tested at the significance level of 0.100. These analyses will be performed on the Intent-To-Treat population. When the treatment-by-subgroup interaction is statistically significant ($p \leq 0.100$) for a specific subgroup, the treatment group differences will be evaluated within each stratum of that subgroup. Analyses stratified by geographic location will be examined for consistency with the overall trial result. A stepwise multivariate regression model with a subset of best baseline predictors for the primary endpoint of mRS will be used for the stratified analyses for consistency with the overall study result with respect to mRS. The time from stroke symptom onset to sheath placement will be evaluated for the MIS group only.

11. Safety Analysis

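### SAP 10.5 cuts age and onset-to-randomization time in two before testing their interaction with treatment, which costs power if the effect changes gradually with either

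*SAP*

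**What the plan says.** SAP 10.5 states that "subgroup analyses will be performed for the primary efficacy variable, 180-day ordinal mRS". Among the listed subgroups, age is cut at 65 and time from symptom onset to randomization is divided at the sample median ("below the median, above the median"). On the model: "The subgroup analysis will be conducted using regression with terms of treatment group and treatment-by-subgroup interaction", with Hemphill Score and hemorrhage location added. On inference: "The primary statistical inference is the treatment-by-subgroup interaction, which is tested at the significance level of 0.100". A significant interaction then triggers evaluation within each stratum.

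The status of these analyses is explicit: "Subgroup comparisons will be considered secondary analyses and will not be adjusted or used for labeling claims". Time from onset to sheath placement is also split at its median, but "The time from stroke symptom onset to sheath placement will be evaluated for the MIS group only", so it has no treatment interaction.

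The stepwise model at the end of SAP 10.5 selects baseline predictors to check consistency of the stratified analyses. It is not described as a test of interaction with a continuous covariate, and no such test appears elsewhere in either document.

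**The concern.** Both variables exist as continuous values: age is needed for eligibility (Protocol 5.1), and a median cannot be found without recorded times. Cutting them first replaces any gradual change of effect with two averages.

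The question matters to this trial. Protocol 10.1 names age among the cohorts in which effect sizes are to be evaluated. Protocol 1.3 and 1.3.2 argue for early and immediate removal of blood, while Protocol 5.1 allows the procedure to start up to 72 hours after the bleed. The meta-analysis described in Protocol 1.3.1 points to surgery within 8 hours and ages 50 to 69. A cut at 65 runs through that age band, and a sample median has no link to 8 hours. Because onset-to-sheath time is confined to the MIS arm, onset-to-randomization time is the only listed timing variable that can show a treatment interaction.

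There is also a small wording gap: a subject exactly at the median falls in neither group.

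**Working it through.** **Inputs.** Maximum 500 and minimum 200 subjects (SAP 5); 2:1 allocation (SAP 3); the MM row of SAP Table 1 (3/10/7/7/14/59%) and odds ratio 1.7 (SAP 2); final one-sided alpha 0.02 (SAP 10.1); interaction level 0.10 (SAP 10.5), whose sidedness is not stated and is taken here as two-sided. The documents give no age or time distribution and no power for any interaction test.

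**1. The plan's own figure.** Shifting the MM row by an odds ratio of 1.7 gives MIS proportions of 5.0/15.3/9.6/8.8/15.6/45.8%, which agree with Table 1 to rounding. Pooled 2:1, they are 0.043, 0.135, 0.087, 0.082, 0.150 and 0.502, and their cubes sum to 0.134. By Whitehead's proportional-odds formula:

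V = 500 × (2/9)/3 × (1 − 0.134) = 32.1, so SE(log OR) = 1/√32.1 = 0.1766.

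Power at one-sided 0.02 = Φ(0.5306/0.1766 − 2.054) = 83%. The stated 81% comes from simulating the adaptive design; a fixed-sample 83% is close, and the small shortfall fits a design with futility stops.

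**2. Continuous versus split, linear gradient.** Let the log odds ratio change by β per SD of a normal covariate that is independent of treatment.

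- Continuous: z = β/0.1766.
- Median split: the halves differ in mean by 2√(2/π) = 1.596 SD, and the difference between two half-sample log odds ratios has SE 2 × 0.1766 = 0.353. So z = 1.596β/0.353, which is 0.798 of the continuous z. Information retained is 0.798² = 2/π = 0.637; 36% is lost.
- Power = Φ(z − 1.645).

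| Subjects | β per SD | Continuous | Split |
|---|---|---|---|
| 500 | 0.2 | 30% | 23% |
| 500 | 0.3 | 52% | 39% |
| 500 | 0.4 | 73% | 56% |
| 500 | 0.5 | 88% | 73% |
| 200 | 0.2 | 18% | 14% |
| 200 | 0.4 | 42% | 31% |

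(At 200 subjects V = 12.8 and SE = 0.279.)

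Simulated proportional-odds likelihood-ratio tests (500 subjects, 250 runs, interaction odds ratio 1.55 per SD) rejected in 77% of runs continuous and 59% split.

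**3. Sensitivity to the unknown distribution.** Information lost is 1 minus the squared correlation between the covariate and its two-group version. All distributions below are assumptions.

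| Assumed covariate | Lost |
|---|---|
| Uniform, median cut | 25% |
| Normal, median cut | 36% |
| Right-skewed time capped at 72 h, median cut | 39% to 47% |
| Exponential, median cut | 52% |
| Age within 18–80, cut at 65: mean 65, SD 10 | 35% |
| mean 62, SD 10 | 40% |
| mean 60, SD 12 | 44% |
| mean 55, SD 12 | 54% |

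Where the continuous test has 80% power, the split has about 51% to 70% across these rows. The range is not a hard bound: a mean age of 50 (SD 12) would put only 10% at 65 or over and lose 67%.

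**4. If the effect steps at the cut.** Take a difference of 0.8 in log odds ratio between the two halves. Split: z = 0.8/0.353 = 2.27, power 73%. Linear on a normal covariate: z = 2.27 × 0.798 = 1.81, power 56%. The advantage reverses exactly.

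**The case against.** The strongest reply is that the comparison depends on the shape of the effect. Step 4 shows that the split wins by the same margin if the effect changes abruptly at the cut, and a spline plot would not recover the power a linear test loses there. This stands, and it makes the point conditional. A step located exactly at 65 or at the sample median is, however, a narrow alternative, and nothing in the documents argues for one.

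Second, the larger gradients are demanding. Around an overall odds ratio of 1.7, 0.4 per SD means 1.7 × e^(−0.8) = 0.76 at −2 SD and 1.7 × e^(0.8) = 3.78 at +2 SD. For modest gradients, or if the trial stops at 200, both tests are weak. This also stands.

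Third, SAP 10.5 uses a formal interaction test at a relaxed level, and grouping suits the aim in Protocol 10.1 of reporting effects within cohorts. That supports keeping the two-group estimates; it does not require the cut variable to carry the test. A median split of a baseline covariate is a fixed rule that does not look at outcomes, and no bias or inflated type I error from it has been shown. Subjects exactly at the median are likely to be few.

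A reader might go further and infer that a fixed third of the information is lost for both variables, that this is the weakest possible analysis, or that a null result will be taken as proof of no dependence. The documents support none of these. They give no distributions, and age is not cut at its median. A more off-center cut, or within-group tests without an interaction test, would be worse. No passage says how a null result would be interpreted.

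**Conclusion.** The point holds as a conditional, minor one. If the treatment effect changes roughly linearly with age or onset-to-randomization time, cutting first costs about 25% to 54% of the information for the interaction test under plausible assumed distributions. At 500 subjects with a normal covariate and a median cut, that means about 73% versus 56% power at 0.4 per SD, and about 30% versus 23% at 0.2 per SD. The power figures also assume proportional odds, the Table 1 distribution and a two-sided 0.10 level. Under a step at the cut the ordering reverses.

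The primary, safety and labeling analyses are untouched. Nor does the point settle how benefit depends on time to evacuation: onset-to-randomization time is a proxy for it, and onset-to-sheath time, observed only in the MIS arm, is outside both this test and the proposed change.

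**What to change.** In SAP 10.5, for age and onset-to-randomization time only:

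- Make the primary interaction inference a test with the covariate continuous: treatment, covariate main effect, and linear treatment-by-covariate interaction on the log-odds scale, alongside Hemphill Score and location. The current model sentence does not name a covariate main effect.
- Add a low-knot spline as a check on linearity, and plot the odds ratio with its confidence interval against the covariate.
- Keep the two-group odds ratios with confidence intervals as descriptive results, reported whatever the interaction p-value. This replaces the significance trigger for these two variables.
- State which group takes values equal to the median.

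The cost is SAP wording and minor programming, with no new data or subjects. The downside is that the linear form is an assumption and would be the weaker test if the effect truly steps at the cut; the spline check and the retained two-group estimates would help to show that.

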11.4. Analysis of Deaths

The Kaplan-Meier product-limit method will be the primary method utilized to assess the mortality rate. With the date of randomization set at Day 0, any death occurring on or before calendar day 30 will be counted as a death. If clinical assessment is missing for a patient who has not died, the patient will be censored at the last follow-up date. Patients who are alive at day 30 will be censored at day 30. The log-rank test will be used to compare the groups. This comparison weights earlier and later differences equally. The time to death will be plotted with confidence intervals at monthly intervals.

Additionally, the death data will be presented as binary deaths. The number of deaths will be presented for each group. A proportional hazards model may be used to account for confounders and center effects, if applicable.

12. Pooling Across Centers

Analyses will be presented by treatment group using data pooled across site. The site analysis will be conducted using an ordinal logistic regression with terms of treatment group and treatment-by-site interaction. This analysis will be performed on the Intent-To-Treat population. The primary statistical inference is the treatment-by-site interaction, which is tested at the significance level of 0.15. When the treatment-by-site interaction is statistically significant ($p \leq 0.15$), the treatment group differences will be evaluated within each site. Adjusted analysis on the primary outcome using key baseline variables will be used for the site analyses for consistency with the overall study result. If the odds ratio of the treatment effect is found to vary by site, then a random-effects model analysis will be performed to assess whether there was significant variance in the primary endpoint according to study site.

13. Lost to Follow-up and Missing Data

Subjects not completing the 180-day follow-up mRS will be imputed for the primary endpoint using the mRS as of the last available follow-up visit (i.e. Day 30, Day 90) and the Bayesian longitudinal model. The median mRS score will be imputed for each patient corresponding to the last mRS value and the longitudinal model posterior distributions. The imputed mRS scores will be utilized in both the interim and final primary analyses.

As a sensitivity analysis, we will also perform the following analyses:

- include only patients with complete 180-day mRS evaluation
- impute patients with missing 180 day mRS as mRS 5/6

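### SAP 10.5 compares stratum odds ratios from a stepwise-adjusted model with an overall odds ratio from a different, unadjusted model

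*SAP*

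**What the plan says.** SAP 10.1 estimates the treatment effect as a cumulative odds ratio from a proportional odds model and says "The primary analysis will be unadjusted"; protocol 10.7 agrees. One further overall model is planned: "A secondary analysis model will include the minimization variables of Hemphill Score and hemorrhage location".

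SAP 10.5 then sets out three things.

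- A formal subgroup inference with the same two fixed covariates: "In addition, Hemphill Score and hemorrhage location will be included in the model", and "The primary statistical inference is the treatment-by-subgroup interaction, which is tested at the significance level of 0.100".
- A separate consistency check: "Analyses stratified by geographic location will be examined for consistency with the overall trial result".
- The model for those stratified results: "A stepwise multivariate regression model with a subset of best baseline predictors for the primary endpoint of mRS will be used for the stratified analyses". The rest of that sentence gives the purpose as consistency with the overall study result on mRS.

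No candidate list, entry or removal rule, or numerical consistency criterion is given. The SAP does not say whether selection is done once or in each stratum, and it plans no overall refit with the selected covariates.

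SAP 12 (and protocol 10.11) follows a related pattern for sites, with unnamed covariates and no mention of stepwise selection: "Adjusted analysis on the primary outcome using key baseline variables will be used for the site analyses for consistency with the overall study result".

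**The concern.** A consistency check needs the same quantity on both sides. Here the stratum odds ratios are conditional on whatever covariates were selected, while the overall odds ratio is conditional on none, or on two others. For a cumulative odds ratio these are different estimands. Conditioning on a prognostic covariate moves the odds ratio away from 1 without any difference in treatment effect.

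Following the plan as written, US and OUS could both show a larger effect than the trial as a whole. A reader could not tell how much of the gap is heterogeneity and how much is the change of model. What is at stake is the reading of a secondary table.

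**Working it through.** **Inputs.** SAP Table 1, MM row: 3/10/7/7/14/59% for mRS 0, 1, 2, 3, 4, 5/6, so cumulative 3, 13, 20, 27, 41%. OR 1.7, N = 500, allocation 2:1, final one-sided test at 0.02 (SAP 2, 3, 10.1). Assumed, because the documents give no value: the strength of the covariates, the stratum split and the selection rule.

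**1. The plan's own figure.** OR 1.7 applied to the MM row gives 5.0/15.3/9.6/8.8/15.6/45.8%, which matches the MIS row after rounding. Whitehead's formula is V = n1·n0·N / [3(N+1)²] × (1 − Σp̄³), with p̄ the 2:1 average of the two rows and Σp̄³ = 0.134:

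- V = 36.89 × 0.866 = 31.95, so SE(log OR) = 1/√31.95 = 0.177.
- Power at 0.02 = Φ(0.531 × 5.65 − 2.054) = Φ(0.946) = 82.8%.
- Simulating 3,000 fixed-size trials (333:167) gives 81.1%.

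The stated 81% is reproduced within 2 points as a fixed design, so the inputs are read correctly. The interim rules were not simulated because they are in a separate report.

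**2. Size of the adjustment effect.** Take logit P(Y ≤ j) = α_j + β·T + σ·x, with x standard normal and the same β in every stratum. Choose each α_j so that the MM row, averaged over x, equals Table 1. Then find the β for which the unadjusted proportional odds fit at 2:1 returns 1.70.

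| SD of prognostic score, σ | Latent R² = σ²/(σ² + π²/3) | Unadjusted OR | Adjusted OR | Ratio | Shift in log OR |
|---|---|---|---|---|---|
| 0.5 | 0.07 | 1.70 | 1.75 | 1.03 | 0.03 |
| 1.0 | 0.23 | 1.70 | 1.88 | 1.11 | 0.10 |
| 1.5 | 0.41 | 1.70 | 2.08 | 1.22 | 0.20 |

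After averaging over x, proportional odds no longer holds exactly, so the result depends slightly on how the cut points are combined. Weighting the cut-point log odds ratios instead of fitting by maximum likelihood gives 1.74, 1.87 and 2.05.

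Hand check: log OR(adjusted) ≈ log OR(unadjusted) × √(1 + 0.346σ²). For σ = 1 this is 0.531 × 1.160 = 0.616, an OR of 1.85; for σ = 0.5 and 1.5 it gives 1.74 and 2.03.

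**3. What the check would show.** 200 trials were simulated per scenario with N = 500, 2:1, a 70/30 split and no heterogeneity. There were eight candidate covariates, four of them prognostic except in the SD 0 scenario, with stepwise entry at p < 0.05 in each stratum. Monte Carlo error is up to √(0.25/200), about 3.5 points.

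| | SD 0 | SD 1.0 | SD 1.5 | SD 2.0 |
|---|---|---|---|---|
| Both stepwise strata above the unadjusted overall OR | 3.5% | 38.5% | 58% | 78.5% |
| Both unadjusted strata above it | 0% | 0.5% | 1% | 1% |
| Both stepwise strata above an overall OR refitted by the same procedure | 3% | 6.5% | 5.5% | 7.5% |
| At least one stepwise stratum outside the overall 95% CI | 23% | 34% | 52.5% | 75% |
| At least one unadjusted stratum outside it | 22.5% | 22% | 22% | 22% |

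The third row isolates the cause. Once the overall odds ratio comes from the same kind of model, most of the artefact goes, even with stepwise selection still in place.

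**4. Against sampling error.** The same formula gives SE(log OR) of 0.21 for a stratum of 350 and 0.32 for one of 150. Shifts of 0.03 to 0.20 are smaller than one standard error of a single stratum. They are systematic, however, and push all strata the same way.

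**The case against.** The strongest reply is that little hangs on this comparison. The formal subgroup inference is the interaction test, which compares strata within one model with fixed covariates, and SAP 10.5 adds "Subgroup comparisons will be considered secondary analyses and will not be adjusted or used for labeling claims". That stands, and it sets the weight of the point.

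Second, the SAP never says outright that the overall result is the unadjusted odds ratio. True, but that is the natural reading, and the alternative in SAP 10.1 has two fixed covariates, so it would still not match a stepwise set.

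Third, adjustment moves every stratum in the same direction and sampling noise is larger. Also true. Non-collapsibility alone does not separate US from OUS or reverse a direction. It opens a gap from the headline figure, which is the comparison that the SAP specifies.

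Three stronger readings are tempting and not supported:

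- A reader might infer that data-driven selection by itself makes strata look inconsistent. With no prognostic covariates it does almost nothing (3.5% and 23% in the SD 0 column), and fixed covariates would create the same gap against an unadjusted overall result.
- A reader might infer that stepwise selection makes the treatment standard errors too small. That is a general worry about selected models; it was not measured here for the treatment coefficient and is not part of this point.
- A reader might infer from SAP 12 that site results are stepwise-adjusted too. That section names no selection method and shares only the adjusted-versus-unadjusted mismatch.

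**Conclusion.** The point holds as a minor one. SAP 10.5, read with SAP 10.1, compares odds ratios from different models, and the gap can be misread as inconsistency. With an identical effect everywhere, an overall 1.70 appears as about 1.75, 1.88 or 2.08 for an assumed prognostic-score SD of 0.5, 1.0 or 1.5: roughly 3%, 11% and 22% larger. The range rests on an assumed normal prognostic score calibrated to Table 1. Some shift is to be expected, since protocol section 10 says that hemorrhage location and Hemphill Score are associated with functional outcome, but the documents do not say how strongly.

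It would go too far to conclude that consistency across strata cannot be assessed. The interaction test at 0.100 does that within one model. The primary test, its alpha and the stated power do not depend on this wording.

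**What to change.** In SAP 10.5, replace stepwise selection with one pre-specified set of baseline covariates already collected. At a minimum this is Hemphill Score and hemorrhage location, which the interaction model and the secondary overall model already use. Report the overall and every stratum odds ratio from that same model. A covariate that defines a stratum drops out within it. Using unadjusted odds ratios on both sides would serve equally well.

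Suggested wording: *Stratum odds ratios, and the overall odds ratio with which they are compared, will be estimated from proportional odds models with the same pre-specified covariates, Hemphill Score and hemorrhage location.*

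In SAP 12, name the covariates and set the adjusted site analysis against an overall odds ratio from a model with the same covariates. Estimate it in a pooled model rather than by separate adjusted fits within each site: 500 patients over 50 sites is about 10 per site, too few for a six-category ordinal model with several covariates. Protocol 10.11 carries the same site text and should be aligned.

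The cost is a wording change, slightly less freedom in choosing covariates, and one additional overall fit to report. No new data are needed.
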